16.0 DATA MANAGEMENT

16.1 Data and Safety Monitoring

The UTSW Simmons Cancer Center (SCC) Data Safety Monitoring Committee (DSMC) is responsible for monitoring data quality and patient safety for all UTSW SCC clinical trials. As part of that responsibility, the DSMC reviews all local serious adverse events in real time as they are reported and reviews adverse events on a quarterly basis. The quality assurance activity for the Clinical Research Office provides for periodic auditing of clinical research documents to ensure data integrity and regulatory compliance.

A detailed description of the Data and Safety Monitoring Plan is available in section X of the Clinical Research Office Operations Manual.

The SCC DSMC meets quarterly and conducts annual comprehensive reviews of ongoing clinical trials, for which it serves as the DSMC of record. The QAC works as part of the DSMC to conduct regular audits based on the level of risk. Audit findings are reviewed at the next available DSMC meeting. In this way, frequency of DSMC monitoring is dependent upon the level of risk. Risk level is determined by the DSMC Chairman and a number of factors such as the patient population to be studied; adequacy of the data management system; and procedures to ensure the safety of study subjects based on the associated risks of the study. Protocol-specific DSMC plans must be consistent with these principles. The following examples can be used to begin developing DSMC plans for individual protocols.

- **High risk** examples include Phase 1 studies; Phase II or III studies where the SCC is the DSMC; gene therapy or recombinant DNA studies; and studies in which the investigator holds the IND.
- **Moderate risk** examples include pilot studies and other Phase II or III studies where the SCC DSMC is not the DSMC of record and which involve a non-FDA approved drug.
- **Low risk** examples include Phase II or III studies involving FDA-approved drugs where the SCC DSMC is not the DSMC of record, or trials, which involve non-therapeutic interventions.
- **Exempt** examples include non-interventional studies, which are exempt from audit requirements outlined above.

17.0 PROTECTION OF HUMAN SUBJECTS

Participation in this trial is voluntary. All patients will be required to sign a statement of informed consent, which must conform to IRB guidelines.

Inclusion of Women and Minorities: Patients of all races, both male and female, will be accepted into the protocol.

Exclusion of Lactating or Pregnant Women: Children have been excluded from this study. Hepatocellular carcinoma is an adult cancer. Thus, the relevance of this drug to the pediatric population has not been established. Lactating and pregnant women are also excluded because of potential anti-proliferative effects of therapy that may be harmful to the developing fetus or nursing infant.

Benefits: It is possible that this treatment will result in shrinkage of hepatocellular carcinoma or in a stabilization of an otherwise progressing disease.

It is not know, of course, whether these or any other favorable events will occur. It is not known whether this treatment will affect overall survival of the patients.

Costs: The patient will be responsible for the costs of standard medical care, including, MRI scans (excluding the MRI scan at week 5 of treatment), all drug administration fees (excluding sessions where bavituximab is given), and all hospitalizations, even for complications of treatment. Bavituximab will be supplied to patients without costs from Peregrine Pharmaceuticals. Patients will not be responsible for the costs of tissue or serum procurement (including image guided biopsies) obtained for research purposes.

Incentives: No incentives will be offered to patients/subjects for participation in this study.

Alternatives: For patients with advanced hepatocellular carcinoma, alternative treatments may include other chemotherapy regimens or loco-regional therapies including transarterial chemoembolization and radiofrequency ablation. At present, no specific treatment approach is considered standard of care for the disease. Patients may be eligible for other investigational studies.

Confidentiality: Every effort will be made to maintain patient confidentiality. Research and hospital records are confidential. Patient's name or any personally identifying information will not be used in reports or publications resulting from this study. The Food and Drug Administration or other authorized agencies (i.e., qualified monitors from UT Southwestern Medical Center, the NCI, etc.), may review patients records and pathology slides, as required.

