3.0 BACKGROUND AND RATIONALE

3.1 Hepatocellular Carcinoma

Hepatocellular carcinoma (HCC) is the fifth most common cancer worldwide and is responsible for more than 500,000 deaths annually. (1) Previously considered uncommon in Western countries, the incidence and mortality of HCC have increased three-fold in the United States over the past two decades. (2) Although complete resection or hepatic transplantation remains the most effective therapies for localized HCC, 50-70% of patients present with advanced disease not amenable to curative surgical approaches. (3,4) Disease that is diagnosed at an advanced stage or with progression after locoregional therapy has a dismal prognosis with a median overall survival of < 12 months mainly due to underlying liver dysfunction and suboptimal treatment options. (2) Ablative therapies are commonly used in this setting but are ineffective for large (>5 cm) or multifocal tumors, both commonly found in advanced disease. (5,6) Hepatic artery chemoembolization may have utility in patients with HCC but there are conflicting reports regarding its efficacy and in advanced disease a survival benefit has not been demonstrated. (7,8)

Systemic Therapy for Advanced Hepatocellular Carcinoma

The use of single agent systemic cytotoxic chemotherapy regimens including

irinotecan, gemcitabine or doxorubicin have historically demonstrated low response rates with little to no clinical efficacy. (9-11) Combination chemotherapy regimens using cytotoxic chemotherapeutic agents have fared no better with response rates ranging from 0% to 40% and limited clinical efficacy. A recent study compared single agent doxorubicin to a combination of cisplatin, interferon, doxorubicin and 5-fluorouracil (PIAF). Despite an improvement in response (10% for doxorubicin vs. 21% for PIAF) the study failed to show an improvement in survival (6.8 vs. 8.6 months, respectively; P=0.83). (12)

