The lack of appropriate traditional chemotherapeutic agents led to the investigation of molecular targeted agents, which have been shown to be efficacious in other tumor models. Sorafenib, an oral multikinase inhibitor that blocks tumor cell proliferation by targeting the Raf/MEK/ERK signaling pathway and exerts an anti-angiogenic effect by targeting the tyrosine kinase receptors, VEGFR-2, VEGFR-3 and PDGF- β , is the first biologically targeted agent to show efficacy in the treatment of advanced stage HCC. (13,14) In a phase III randomized controlled trial (SHARP trial), patients with advanced hepatocellular carcinoma (not eligible for surgical resection or transplantation) and preserved liver function (Child-Pugh A score) were randomly assigned to either systemic sorafenib or placebo. There was a significantly longer survival and radiologic time to progression (TTP) outcome in the cohort of patients that received sorafenib with little or no toxicity. Grade 3 drug related events included diarrhea (8% in the sorafenib group vs. 2% in the placebo group), hand-foot skin reaction (8% vs. 1%), hypertension (2% vs. 1%) and abdominal pain (2% vs. 1%); there were no grade 4 drug-related adverse events in any of these categories in either study group. Currently sorafenib is the only drug that has FDA approval for the systemic treatment of HCC. Although sorafenib is the current standard of care for patients with advanced HCC, it prolonged radiologic time to progression less than 3 months when compared to best supportive care: 5.5 months versus 2.8 months, respectively. Overall survival was prolonged less than 3 months compared to best supportive care, 10.7 months versus 7.9 months, respectively. (14) Although systemic treatment with sorafenib shows statistically significant clinical efficacy, its overall benefit is modest. The complexity of HCC would appear to lend itself to escape mechanisms from the sorafenib-specific blockade of the RAF-MEK-ERK and VEGFR/PDGF pathways, thereby promoting tumor proliferation and neo-angiogenesis through alternative means. Such a mechanism would explain why certain patients fail to benefit from sorafenib therapy and provides the rationale for combining sorafenib with other chemotherapeutic agents.

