3.3 Study Rationale

Combination therapy consisting of bavituximab and sorafenib is attractive for patients with advanced HCC for the following reasons:

1. Based on the previously mentioned SHARP trial, sorafenib is the first drug in the modern era to receive FDA approval for treatment of advanced HCC. Although sorafenib is now established as part of standard therapy, its overall benefit is modest, and advanced HCC remains uniformly fatal. Due to the multiple escape mechanisms for angiogenesis inhibition in HCC, a logical next step would be to combine sorafenib with other biologic or chemotherapeutic agents.
2. Externalized PS is a desirable marker for tumor targeting for several reasons: PS is specifically and abundantly expressed on tumor vascular endothelium; it is present on a high percentage of tumor endothelial cells in a variety of solid tumors; it is absent from non-tumor vasculature; and it is expressed on the luminal side of tumor vascular endothelium, which is readily accessible for targeting drugs. Combining bavituximab, an angiogenesis inhibitor, with sorafenib, an angiogenesis inhibitor with a different mechanism, may prevent signaling escape mechanisms seen with either drug if given individually.
3. Data from preclinical studies have demonstrated that sorafenib therapy increases PS exposure on tumor vascular endothelium in a HCC tumor model. The increase of PS exposure will amplify the target for bavituximab and should increase tumor vessel destruction producing increased treatment efficacy.

It is our hypothesis that combination therapy with bavituximab and sorafenib will provide greater clinical efficacy than either agent alone with minimal toxicity.

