10.1 Correlative Studies (Phase II patients only)

Pathology Correlative Studies

A major obstacle to molecularly targeted chemotherapeutic agents has been obtaining relevant tumor tissue to measure the agents' biologic effects on target molecules or cellular pathways within the tumor. The utilization of sequential tumor biopsies to obtain tissue following treatment is well established in breast and colorectal carcinoma. (30) However, sequential tumor biopsies of liver tumors are less established due to a fear of procedural complications. The fear of bleeding events following liver biopsy of HCC appears unfounded and based on anecdotal evidence. A large, multi-institutional trial where patients with advanced chronic hepatitis C underwent sequential liver biopsies demonstrated 16 cases (0.6%) of bleeding following 2740 liver biopsies. There were no deaths from peri-procedural bleeding and a platelet count under 60000 was identified as a risk factor. (31) Two large published series of core needle biopsy of HCC as a diagnostic measure report bleeding events in less than 1% of patients with no reported mortalities. In both series capsular location of HCC was associated with increased incidence of bleeding event. (32,33)

In this study all patients will potentially undergo up to two image-guided (either CT or ultrasound) core needle biopsy of a single site of HCC at baseline (for clinical care) and between five and six weeks after the initiation of bavituximab. In addition to the patients receiving treatment as part of this clinical trial, patients identified from the HCC clinics at UT Southwestern who are initiating sorafenib monotherapy will undergo biopsies at baseline and between five and six weeks after initiation. These biopsies are not mandatory to initiate or continue with therapy and are subject to a separate informed consent. To increase patient safety the following conditions must be met prior to liver biopsy:

- Platelet count $\geq 70,000$
- INR ≤ 1.8
- Target lesion not subcapsular in nature as determined by the participating interventional radiology team
- Sorafenib will be discontinued for a period of 24-48 hours prior to biopsy

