18.0 INFORMED CONSENT PROCEDURES

Before protocol-specified procedures are carried out, consenting professionals will explain full details of the protocol and study procedures as well as the risks involved to patients prior to their inclusion in the trial. Patients will also be informed that they are free to withdraw from the study at any time. All patients must sign an IRB-approved consent form indicating their consent to participate. This consent form will meet the requirements of the code of federal regulations, and the IRB of this center. The consent form will included the following:

1. The nature and objectives, potential toxicities and benefits of the intended study.
2. The length of therapy and the likely follow-up required.

3. Alternatives to the proposed therapy. This will included available standard and investigational therapies. In addition, patients will be offered an option of supportive care.
4. The name of the investigator (s) responsible for the protocol.
5. The right of the patient to accept or refuse treatment and to withdraw from participation in the study.

Each patient and consenting professional will sign the consent form in triplicate. One original signed consent form will become part of the patient's medical record, another original signed consent form will be stored in the patient's research file, and the third original signed consent form will be given to the patient.

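### Section 17.0 tells patients that nothing is standard of care and leaves out sorafenib alone, contradicting Sections 3.1 and 3.3

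*Combined protocol and SAP*

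**What the plan says.** Section 17.0, under Alternatives, says that "alternative treatments may include other chemotherapy regimens or loco-regional therapies including transarterial chemoembolization and radiofrequency ablation". It then states: "At present, no specific treatment approach is considered standard of care for the disease". It adds that patients may qualify for other investigational studies. Sorafenib alone is not mentioned.

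Section 3.1 opens its account of sorafenib's modest benefit with "Although sorafenib is the current standard of care for patients with advanced HCC". Just before that it says: "Currently sorafenib is the only drug that has FDA approval for the systemic treatment of HCC". Section 3.3 gives the same position in the rationale for the combination: "Although sorafenib is now established as part of standard therapy".

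Section 18.0 sets out what the consent form must contain. On alternatives to the proposed therapy it says: "This will included available standard and investigational therapies". It also requires that supportive care be offered.

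**The concern.** Both study drugs are given together, and one of them is already marketed for this disease. For an eligible patient the practical question is therefore whether to take sorafenib with an investigational antibody or sorafenib without it. Joining adds weekly 90-minute infusions with steroid and antihistamine premedication (Section 5.1), and the infusion reactions and possible thromboembolic risk described in Section 12.2.

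The section on protection of participants does not present that choice. It denies that any standard exists and leaves out the alternative closest to the study treatment. If that text were carried into a consent form, a patient could conclude that enrolling is the way to obtain effective systemic therapy. What is at stake is the accuracy of disclosure. The statistical inference is not touched.

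**Working it through.** No arithmetic bears on the contradiction, so the check is a comparison of the text.

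1. **Same disease, same point in time.** Section 17.0 speaks of advanced hepatocellular carcinoma in the present. So does Section 3.1 ("Although sorafenib is the current standard of care for patients with advanced HCC"). Neither limits its statement to a subgroup, so a difference in population or date does not explain the conflict. If Section 3.1 is right, the sentence in Section 17.0 is wrong.

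2. **Is sorafenib alone an option by the protocol's own account?** Four places indicate that it is.
   - Section 5.2 describes the tablets as commercially available.
   - Section 10.1 draws a comparison group from routine care at the study centre: "patients identified from the HCC clinics at UT Southwestern who are initiating sorafenib monotherapy will undergo biopsies at baseline".
   - Sections 4.2.1 and 11.0 allow phase I patients to go on with sorafenib after the single study cycle, at the treating oncologist's discretion.
   - Section 15.1 takes its phase II benchmark, a median time to progression of 5.5 months, from patients treated with sorafenib. The trial is thus judged against the option that the Alternatives text omits.

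3. **What does Section 3.1 say of the alternatives that are listed?** Single-agent cytotoxic drugs have "historically demonstrated low response rates with little to no clinical efficacy", and combinations are also said to have limited efficacy. Ablation is described as commonly used, but ineffective for large or multifocal tumors. Chemoembolization is said to have possible utility with conflicting reports, and no survival benefit shown in advanced disease. For sorafenib, Section 3.1 reports:
   - median overall survival of 10.7 against 7.9 months, a difference of 10.7 − 7.9 = 2.8 months;
   - time to progression of 5.5 against 2.8 months, a difference of 5.5 − 2.8 = 2.7 months.

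   These figures come from a placebo-controlled phase III trial in Child-Pugh A patients. Section 6.1 of this protocol also admits B7, so they cannot be assigned to every participant.

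4. **Reach.** The Alternatives paragraph does not distinguish between phases. Planned enrolment in Section 1.0 is 9–18 patients in phase I and 38 in phase II: 9 + 38 = 47 and 18 + 38 = 56.

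5. **Against Section 18.0.** That section asks for the available standard therapies. An author who takes the answer from Section 3.1 names sorafenib. One who takes it from Section 17.0 writes that there is none.

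**The case against.** The strongest reply is that Section 18.0, not Section 17.0, governs the consent form. It already requires standard therapies to be disclosed, under IRB approval, and nothing says that the form is drafted from Section 17.0. The list in Section 17.0 is introduced as what alternatives may include, so it is not exhaustive and does not forbid mention of sorafenib. Recruitment under Section 7.0 follows a discussion of the disease and an initial treatment plan, at a centre whose clinics already start patients on sorafenib alone.

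Much of this stands, and it rules out several stronger readings that a reader might infer.

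- *Patients were misinformed.* The sample consent form is listed as Appendix D but was not in the reviewed file, so this cannot be shown.
- *Sections 17.0 and 18.0 cannot both be followed.* They can. Section 17.0 describes and does not instruct, and staff can disclose sorafenib without breaching it.
- *Every misled patient would also accept research biopsies.* Section 10.1 restricts the correlative studies to phase II and says that the biopsies are not a condition of starting or continuing therapy. Section 4.2.2 makes the second biopsy optional.
- *Consent would differ between sites.* The documents describe an IRB-approved form, and Section 19.0 has satellite sites send its signed signature page for review. They give no evidence of variation.

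What the reply does not reach is the sentence itself. An open-ended list can excuse an omission, but not a flat denial that any standard exists. The word *other* before chemotherapy regimens also points away from the study drugs. A general duty in Section 18.0 does not correct a specific statement to the contrary one section earlier.

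**Conclusion.** The contradiction holds. Section 17.0 denies a standard of care that Section 3.1 affirms and Section 3.3 supports, and it omits sorafenib alone, which the protocol elsewhere shows to be marketed and in use at the study centre. The effect on patients is conditional: a consent form that copied Section 17.0 would misinform them about their main alternative, and whether the actual form does so is unknown.

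This should be fixed, because it is an inaccurate statement in the section on patient protection and it applies to all 47 to 56 planned patients. It does not rank higher than that. Section 18.0 already asks for the right disclosure, and no endpoint, sample size or analysis changes. The conclusion relies only on the protocol's own description of sorafenib's status. It does not depend on the size of the survival or progression benefit, which was observed in Child-Pugh A patients only.

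**What to change.** Reconcile the Alternatives paragraph of Section 17.0 with Sections 3.1, 3.3 and 18.0:

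- delete the sentence that denies any standard of care;
- state that sorafenib alone, described in Section 3.1 as the current standard and FDA-approved, is available without joining the study;
- keep chemotherapy, loco-regional therapy and other studies as further alternatives, and add supportive care, as Section 18.0 requires;
- if benefit figures are quoted, say that they come from a trial in Child-Pugh A patients.

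Then check the consent form against the corrected text and amend it if it repeats the old statement.

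The cost is a wording amendment and an IRB submission. A few patients may choose sorafenib off study, which could slow accrual slightly.

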17.1 Privacy

It is the responsibility of the research staff to endure that protocol subjects receive the UT Southwestern Medical Center Notice of Privacy Practices.

17.2 Adverse Events

Adverse Events will be reported as indicated by the appropriate following table (see below).

Definition

An adverse event is defined as any untoward or unfavorable medical occurrence in a human research study participant, including any abnormal sign (for example, abnormal physical exam or laboratory finding), symptom, clinical event, or disease, that occurs during the subject's participation in the research, whether or not it is considered related to the subject's participation in the research.

Adverse events encompass clinical, physical and psychological harms. Adverse events occur most commonly in the context of biomedical research, although on occasion, they can occur in the context of social and behavioral research. Adverse events may be expected or unexpected.

Severity

Adverse events will be graded by a numerical score according to the defined NCI Common Terminology Criteria for Adverse Events (NCI CTCAE) and version number specified in the protocol. Adverse events not specifically defined in the NCI CTCAE will be scored on the Adverse Event log according to the general guidelines provided by the NCI CTCAE and as outlined below.

- Grade 1: Mild
- Grade 2: Moderate
- Grade 3: Severe or medically significant but not immediately life threatening
- Grade 4: Life threatening consequences
- Grade 5: Death related to the adverse event

Serious Adverse Events

ICH Guideline E2A and the UTSW IRB define serious adverse events as those events, occurring at any dose, which meets any of the following criteria:

- Results in death
- Immediately life-threatening
- Results in inpatient hospitalization or prolongation of existing hospitalization
- Results in persistent or significant disability/incapacity
- Results in a congenital anomaly/birth defect
- Based upon appropriate medical judgment, may jeopardize the subject's health and may require medical or surgical intervention to prevent one of the other outcomes listed in this definition.

Note: A “Serious adverse event” is by definition an event that meets *any* of the above criteria. Serious adverse events may or may not be related to the research project. A serious adverse event determination does not require the event to be related to the research. That is, both events completely unrelated to the condition under study and events that are expected in the context of the condition under study may be serious adverse events, independent of relatedness to the study itself. As examples, a car accident requiring overnight hospitalization would be a serious adverse event for any research participant; likewise, in a study investigating end-stage cancer care, any hospitalization or death would be a serious adverse event, even if the event observed is a primary clinical endpoint of the study.

Unanticipated Problems:

The term “unanticipated problem” is found, but not defined in the regulations for the Protection of Human Subjects at 45 CFR 46, and the FDA regulations at 21 CFR 56. Guidance from the regulatory agencies considers unanticipated problems to include any incident, experience, or outcome that meets *each* of the following criteria:

- Unexpected (in terms of nature, severity or frequency); **AND**
 - Definitely, probably, *or possibly related* to participation in the research; **AND**
 - Serious or a possible unexpected problem in that the research *places subjects or others at a greater risk of harm than was previously known or recognized.*
- Note: Any serious adverse event would always suggest a greater risk of harm.

Follow-up

All adverse events will be followed up according to good medical practices.

Reporting

Local unanticipated problems require expedited reporting, are submitted to the UTSW IRB through the UTSW eIRB and to the SCC DSMC Coordinator. Hardcopies or electronic versions of the eIRB report; FDA Form #3500A forms, or other sponsor forms, if applicable; and/or any other supporting documentation available should be forwarded to the DSMC Coordinator. The DSMC Coordinator forwards the information onto the DSMC Chairman who determines if immediate action is required. Follow-up eIRB reports, and all subsequent SAE documentation that is available are also submitted to the DSMC Chair who determines if further action is required.

All local serious adverse events which occur on research subjects on protocols for which the SCC is the DSMC of record require reporting to the DSMC regardless of whether IRB reporting is required. Hardcopies or electronic versions of the FDA Form #3500A forms, or other sponsor forms, if applicable; and/or any other supporting documentation available should be forwarded to the DSMC Coordinator.

If the event occurs on a multi-institutional clinical trial coordinated by the Cancer Center, the DOT Manager or lead coordinator ensures that all participating sites are notified of the event and resulting action, according to FDA guidance for expedited reporting. DSMC Chairperson reviews all serious adverse events within upon receipt from the DSMC Coordinator. The DSMC Chairperson determines whether action is required and either takes action immediately, convenes a special DSMC session (physical or electronic), or defers the action until a regularly scheduled DSMC meeting.

Written reports to:UTSW SCC Data Safety Monitoring Committee Coordinator

Email: [contact]

[contact] or deliver to [name]

UTSW Institutional Review Board (IRB)

Submit via eIRB with a copy of the final sponsor report as attached supporting documentation

1. SAEs

Local serious adverse events (SAEs) for studies where SCC DSMC is the DSMC of record require reporting to the DSMC coordinator within 2 working days of PI awareness, or as described in the protocol.

2. Unanticipated Problems

Local unanticipated problems require reporting to the UTSW IRB within 2 working days of PI awareness of the event.

Unanticipated problems, including those that occur as non-local events, require reporting to the UTSW IRB within 10 working days of PI awareness of the event.

For further guidance for Investigators regarding safety reporting requirements for INDs and BA/BE studies, refer to FDA Draft Guidance document:

<http://www.fda.gov/downloads/Drugs/GuidanceComplianceRegulatoryInformation/Guidances/UCM227351.pdf>

Fax reports to study sponsor at:

IST Clinical Program Manager
Peregrine Pharmaceuticals, Inc.
[contact]

